9.5. Serious Adverse Events Reporting Procedure For Investigators

All AEs, AESIs, events of overdose, and SAEs will be reported in the eCRF. Any SAEs after signing the appropriate ICF should be reported until 40 days (+7 days) after the last dose of the study drug. Any SAEs directly related to a tumor biopsy procedure performed after signing the appropriate Tissue Screening ICF or Tissue Collection ICF should be reported according to the Adverse Event Reporting Requirements section. Any serious, untoward event that may occur subsequent to the 40-day (+7 days) follow-up reporting period that the Investigator assesses as related to study drug should also be reported and managed as an SAE.

Serious events that are also efficacy endpoints (disease progression) will be exempted from SAE processing and expedited reporting. Disease progression should not be reported as an AE/SAE. However, if a subject dies from disease progression with no other immediate causes, “disease progression” should be reported as an SAE and captured on the AE eCRF.

The following types of events should be reported by the Investigator in electronic data capture (EDC) within 24 hours of awareness:

- SAEs (see Section [9.4.2](#) for definition)
- All potential ILD cases should be reported within 24 hours; including both serious and non-serious potential ILD cases (potential ILD is defined by the Event Adjudication Site Manual List of PTs) (see Section [9.3.1](#) for details)
- All hepatic events (both serious and non-serious, and clinical laboratory results) that meet criteria of elevated ALT or AST $\geq 3 \times$ ULN and an elevated total bilirubin $> 2 \times$ ULN that may occur simultaneously or at different time points during the study should be reported as an AE (serious or non-serious) and as an AESI, regardless of whether these hepatic events are symptomatic, lead to study drug discontinuation, dose reduction or dose delay, require corrective treatment, constitute an AE in the Investigator’s clinical judgment and/or are related to disease progression (see Section [9.3.2](#) for details).
- Overdose (see Section [9.5.1](#) for a definition)

All events (serious and non-serious) must be reported with Investigator’s assessment of the event’s seriousness, severity, and causality to the study drug. A detailed narrative summarizing the course of the event, including its evaluation, treatment, and outcome should be provided for SAEs and AESIs. Specific or estimated dates of event onset, treatment, and resolution should be included when available. Medical history, concomitant medications, and laboratory data that are relevant to the event should also be summarized in the narrative. For fatal events, the narrative should state whether an autopsy was or will be performed and include the results if available. Source documents (including medical reports) will be retained at the study center and should not be submitted to the Sponsor for SAE reporting purposes.

Additional relevant information regarding the AESIs of ILD, and all hepatic events that meet the criteria of an elevated ALT or AST $\geq 3 \times$ ULN and an elevated total bilirubin $> 2 \times$ ULN that may occur simultaneously or at different time points during the study for the U3-1402 clinical program, regardless of seriousness, is to be collected through the targeted questionnaires within the clinical study database.

Urgent safety queries and follow-up information such as those upgraded to fatal/life threatening case must be followed up and addressed promptly. The investigator will submit any updated SAE data to the sponsor and/or CRO within 24 hours of receipt of the information. Other follow-up information and response to non-urgent safety queries should be combined for reporting to provide the most complete data possible within each follow-up. In the event that an eCRF is unavailable, report SAEs, overdoses, potential cases of ILD, and hepatic events that meet criteria of elevated ALT or AST $\geq 3 \times$ ULN and an elevated total bilirubin $> 2 \times$ ULN on a Serious Adverse Event Report (SAVER) form. All completed SAVER forms must be signed by the Investigator and e-mailed or faxed to the Sponsor or the CRO using the provided fax transmittal form and the appropriate fax number provided for your country. Once EDC becomes available, please enter events reported on the SAVER Form into the eCRF as soon as possible. Please refer to the eCRF Completion Guide for additional instructions.

Please call the local SAE Hotline (see Study Manual) or your study monitor for any questions on SAE reporting.

9.5.1. Overdose

An overdose is defined as the accidental or intentional administration of any dose of a product that is considered both excessive and medically important. An “excessive and medically important” overdose includes any overdose in which an SAE, a non-serious AE, or no AE occurs and is considered by the Investigator as clinically relevant (ie, it poses an actual or potential risk to the subject). All occurrences of overdose must be reported to the CRO or Sponsor within 24 hours of awareness. Overdose will be reported via the SAVER form or eCRF.

9.6. Pregnancy

The Sponsor must be notified of any female subject who becomes pregnant while receiving or within 7 months of the last dose of U3-1402. The Sponsor must be notified of any male subject whose female partner becomes pregnant while the subject is receiving, or within 4 months of discontinuing, U3-1402.

Although pregnancy is not technically an AE, all pregnancies must be followed to conclusion to determine their outcome. If a pregnancy is reported, the Investigator should inform the Sponsor within 24 hours of learning of the pregnancy.

This information is important for both drug safety and public health concerns. It is the responsibility of the Investigator, or designee, to report any pregnancy in a female subject or partner of a male subject using the Exposure In Utero (EIU) Reporting form. Please contact your study monitor to receive the EIU Reporting Form upon learning of a pregnancy. The Investigator should make every effort to follow the female subject or partner of a male subject (upon obtaining written consent from partner) until completion of the pregnancy and complete the EIU Reporting Form with complete pregnancy outcome information, including normal delivery or induced abortion. Any adverse pregnancy outcome, either serious or non-serious, should be reported in accordance with study procedures. If the outcome of the pregnancy meets the criteria for immediate classification as an SAE (ie, post-partum complications, spontaneous or induced abortion, stillbirth, neonatal death, or congenital anomaly, including that in an aborted fetus), the Investigator should follow the procedures for reporting SAEs.

Pregnancy Test

For women of childbearing potential (as defined in Section 4.1): document the results of a negative serum pregnancy test. For eligibility, if not performed as a part of routine care within 72 hours prior to Cycle 1 Day 1, a serum pregnancy test must be performed with the results available ([Table 13.1](#)). A positive urine pregnancy test must immediately be confirmed using a serum test. Repeat pregnancy test (urine or serum per institutional guidelines) must be performed 72 hours before infusion at each cycle and at the EOT visit.

A female is considered of childbearing potential following menarche and until becoming postmenopausal (no menstrual period for a minimum of 12 months) unless permanently sterile (undergone a hysterectomy, bilateral salpingectomy or bilateral oophorectomy) with surgery at least 1 month before the first dose or confirmed by FSH test ($FSH >40$ mIU/mL and estradiol <40 pg/mL [<147 pmol/L] is confirmatory). Females on hormone replacement therapy (HRT) and whose menopausal status is in doubt will be required to use 1 of the contraception methods outlined for women of childbearing potential if they wish to continue their HRT during the study. Otherwise, they must discontinue HRT to allow confirmation of post-menopausal status prior to the first dose of U3-1402 treatment. For most forms of HRT, at least 2 to 4 weeks must elapse between the cessation of therapy and the blood draw; this interval depends on the type and dosage of HRT. Following confirmation of their post-menopausal status, they can resume use of HRT during the study without use of a contraceptive method.

9.7. Notifying Regulatory Authorities, Investigators, and Institutional Review Board/Ethics Committee

Daiichi Sankyo and/or CRO will inform Investigators and regulatory authorities of any suspected unexpected serious adverse reactions occurring in study sites or other studies of U3-1402, as appropriate per institutional and/or local reporting requirements.

Daiichi Sankyo and/or CRO will comply with any additional local safety reporting requirements. The Investigator will assess if an AE is to be considered “unexpected” based on the “Reference Safety Information” section in the current IB.²⁶

9.8. Clinical Laboratory Evaluations

Clinical laboratory measurements will be conducted at the local laboratory. The following items will be measured. For clinical laboratory parameters, the reference range of the institution that performs the measurements will be used. Refer to the Schedule of Events ([Table 13.1](#)) for timing of these assessments.

Table 9.1: Clinical Laboratory Tests

| Laboratory tests | Parameters |
|---------------------------------|---|
| Hematology | Red blood cell count, hemoglobin, hematocrit, platelet count, white blood cell count, mean platelet volume (if available), reticulated platelet fraction (if available), and differential white blood cell count (absolute and percent) (ie, neutrophils, lymphocytes, monocytes, eosinophils, basophils) |
| Blood Chemistry | Total protein, albumin, ALP, ALT, AST, bicarbonate, TBL, direct bilirubin, indirect bilirubin, BUN/urea, calcium, chloride, creatinine, LDH, magnesium, potassium, sodium, CEA ^a , CA19-9 ^a , and CRP ^a |
| Coagulation (only at screening) | Prothrombin time or prothrombin time-international normalized ratio, and activated partial thromboplastin time/partial thromboplastin time |
| Urinalysis | Protein, glucose, blood, bilirubin, glucose, ketone bodies, leukocyte esterase, occult blood, pH, urobilinogen, microscopic assessment of urine sediment (casts, RBC, WBC), and specific gravity |

ALP = alkaline phosphatase; ALT = alanine aminotransferase; AST = aspartate aminotransferase; BUN = blood urea nitrogen; CA 19-9 = cancer antigen 19-9; CEA = carcinoembryonic antigen; CRP = C-reactive protein; LDH = lactate dehydrogenase; RBC = red blood cell; TBL = total bilirubin; WBC = white blood cell

^a Assessed at the central laboratory

In addition, a pregnancy test (serum) for all female subjects of childbearing potential must be performed during the Screening Period and at the visits (serum or urine) indicated in the Schedule of Events. A positive urine pregnancy test result must be confirmed immediately using a serum test.

All laboratory values must be appraised by the Investigator as to clinical significance and used to take appropriate clinical management measures. All abnormal laboratory values considered clinically significant by the Investigator should be recorded on the AE eCRF. If the abnormal laboratory value constitutes an SAE, it should be reported by the Investigator with a targeted questionnaire that is in-built as an eCRF or a SAVER form within 24 hours of awareness and other relevant procedures must be followed (see Section 9.5). Abnormal laboratory values (NCI-CTCAE Grade 3 or 4) occurring during the clinical study will be followed until repeat test results return to normal (or baseline), stabilize, or are no longer clinically significant.

9.9. Vital Signs

Vital sign measurements will include systolic and diastolic blood pressure, pulse rate, respiratory rate, and body temperature.

Blood pressure and pulse rate should be measured after the subject has rested in a supine position for 5 minutes.

9.10. Electrocardiograms

Standard supine/semi-recumbent 12-lead ECG prior to blood draws and will be performed as described in the Schedule of Events (Table 13.1). The ECG will be measured after the subject has rested supine for at least 10 minutes prior to the ECG assessment. ECGs must be recorded

on an ECG machine and reviewed by the Investigator or delegated physician for the presence of abnormalities. The same test must be used for Screening, EOT, and as clinically indicated.

Abnormal, clinically relevant findings occurring post-baseline will be reported as AEs. Whether or not the measurement is performed, the date the ECG is to be performed, heart rate, PR interval, RR interval, QRS duration, QT interval, QTcF interval, and results will be recorded in the eCRF.

9.11. Physical Examinations

Physical examination findings including ECOG PS will evaluate the following body systems/organs: general appearance; dermatological; head and eyes; ears, nose, mouth, and throat; pulmonary; cardiovascular; abdominal; genitourinary (optional); lymphatic; musculoskeletal/extremities; and neurological. Weight and height will also be recorded in kilograms and centimeters, respectively.

9.12. Other Safety Assessments

Cardiac assessments:

- LVEF
 - LVEF will be measured by either ECHO or MUGA, as described in the Schedule of Events ([Table 13.1](#)). All ECHO/MUGA assessments must be evaluated by the Investigator or delegate. The same modality (ECHO or MUGA) should be used for the subject throughout the study.
 - Refer to Section [13.5](#) for the NYHA Functional Capacity and Objective Assessment.

Ophthalmologic assessments:

- Ophthalmologic assessments will include a visual acuity test (ETDRS, Snellens, or Landolt), slit lamp examination, fundoscopy, and tonometry as indicated in the Schedule of Events (Section [13.1](#)). All ophthalmologic assessments must be evaluated by an ophthalmologist or other qualified practitioner. More frequent examinations may be performed at the discretion of the Investigator and if indicated.

Pulmonary assessments:

- SpO₂ should be measured along with tumor assessments per Investigator discretion and as indicated in the Schedule of Events (Section [13.1](#)). Additional testing to investigate pulmonary disorders may be performed, eg, chest radiograph, functional/blood-gas examination, pulmonary function testing, or serological examinations, at the Investigator's discretion as described in [Table 5.2](#). An ILD AC has been set up for this study. Additional details regarding the ILD AC are available in Section [9.3.1.1](#).

10. OTHER ASSESSMENTS

10.1. Patient Reported Outcomes

Not applicable.

10.2. Pharmacoeconomic Assessments

Not applicable.

11. STATISTICAL CONSIDERATIONS

11.1. General Statistical Considerations

The primary analysis DCO will occur when all subjects have either a minimum of 9 months follow-up or have discontinued from the study earlier. The DCO may be shifted if emerging data indicate responses are occurring at a different time. The final analysis will occur when all subjects have discontinued from the study for any reason. The primary analysis will be included in the CSR.

Descriptive statistics on continuous data will include mean, median, standard deviation, and range (as well as geometric means and geometric coefficient of variation for PK parameters), while categorical data will be summarized using frequency counts and percentages. Graphical summaries of the data may be presented.

Assessments of change from baseline to post-treatment or the ratio of post-treatment to baseline will include only those subjects with both baseline and post-treatment measurements. The last non-missing value of a variable taken before start of study treatment will be used as the baseline value, unless otherwise specified. In general, missing or dropout data will not be imputed for the purpose of data analysis, unless otherwise specified.

A detailed Statistical Analysis Plan (SAP) describing the methodology to be used in the final analysis will be prepared and finalized before database lock.

11.2. Statistical Hypothesis

No statistical testing is planned for this study.

11.3. Sample Size Determination

In Part 1 of the study, approximately 36 subjects will be evaluated in the two cohorts. If both Cohort 1 and Cohort 2 advance to Part 2 of the study, approximately 44 additional subjects will be enrolled in Part 2 (regardless of HER3 IHC status). In such a circumstance, approximately 80 subjects will be enrolled in total. If only Cohort 1 advances to Part 2 of the study, approximately 44 additional subjects will be enrolled in Part 2. In such circumstance, approximately 80 subjects will be enrolled in total (68 of 80 subjects will have HER3 high expressing tumors).

The total sample size is shown in [Table 11.1](#).

Table 11.1: Total Sample Size Pre- and Post-futility Analysis

| | Scenario 1 Enrollment continues in both Cohorts | | Scenario 2 Enrollment continues in Cohort 1 only | |
|---------------------------------------|--|-----------------|---|----------|
| | Cohort 1 | Cohort 2 | Cohort 1 | Cohort 2 |
| Futility decision per cohort | Go | Go | Go | Stop |
| Sample size up to futility | 24 | 12 | 24 | 12 |
| Additional sample size after futility | | 44 ^a | 44 | NA |
| Cohort sample size | | 80 ^a | 68 | 12 |
| Total sample size for the study | | 80 ^a | | 80 |

HER3 = human epidermal growth factor receptor 3; IHC = immunohistochemistry; NA = not applicable

^a All comers will be enrolled regardless of HER3 IHC status

If the criteria to continue enrollment are not met at interim futility analysis in either cohort, further enrollment will be stopped. In this scenario, the total sample size for the study will be approximately 36 subjects (Cohort 1: 24 subjects, Cohort 2: 12 subjects).

Table 11.2 presents the minimum number of responders at various sample sizes for the 95% exact CIs lower bound to be above 5%.

The clinically meaningful ORR is considered as 20% and the ORR based on historical data is considered as 5%.^{9,10}

With a sample size of 68 subjects, if 8 responses are observed, the observed ORR will be 11.8% with a 95% exact confidence interval (CI) of (5.2%, 21.9%). The probability of observing 8 or more responders in 68 subjects is approximately 97.4% when the true ORR is 20%. If the true ORR is 5%, the probability of observing 8 or more responders in 68 subjects is approximately 2%.

With a sample size of 80 subjects, if 9 responses are observed, the observed ORR will be 11.25% with a 95% exact CI of (5.3%, 20.3%). The probability of observing 9 or more responders in 80 subjects is approximately 98.7% when the true ORR is 20%. If the true ORR is 5%, the probability of observing 9 or more responders in 80 subjects is approximately 1.8%.

Table 11.2: Statistical Properties for Different Sample Sizes

| N | Number of Responders (x) | Observed ORR | 95% Exact CI | P (X ≥ x p = 0.2) | P (X ≥ x p = 0.05) |
|----|--------------------------|--------------|---------------|---------------------|----------------------|
| 68 | 8 | 11.8% | (5.2%, 21.9%) | 97.4% | 2.0% |
| 80 | 9 | 11.25% | (5.3%, 20.3%) | 98.7% | 1.8% |

CI = confidence interval; ORR = objective response rate.

Table 11.3 summarizes the exact two-sided 95% CIs for the observed ORR ranging from 5% to 20% approximately (with an increment of approximately 5%) at various sample sizes.

Table 11.3: Exact Confidence Interval for Different Observed Objective Response Rates

| N=68 | | N=80 | |
|--|----------------|--|----------------|
| Number of Responders (Observed ORR) | 95% Exact CI | Number of Responders (Observed ORR) | 95% Exact CI |
| 4 (5.9%) | (1.6%, 14.4%) | 4 (5%) | (1.4%, 12.3%) |
| 7 (10.3%) | (4.2%, 20.1%) | 8 (10%) | (4.4%, 18.8%) |
| 11 (16.2%) | (8.4%, 27.1%) | 12 (15%) | (8%, 24.7%) |
| 14 (20.6%) | (11.7%, 32.1%) | 16 (20%) | (11.9%, 30.4%) |

CI = confidence interval; ORR = objective response rate.

All calculations were performed using the SAS 9.4 software.

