11.6. Interim Analyses

For each study cohort, review of the preliminary data from Part 1 will be used to determine whether to open Part 2. The decision to advance from Part 1 to Part 2 will be made separately in Cohort 1 and Cohort 2; the interim futility analysis will be conducted with approximately 24 subjects in Cohort 1 and approximately 12 subjects in Cohort 2 after all subjects have had the opportunity to complete two tumor assessments. The tumor assessment period may be extended if emerging data show responses are occurring later, or if the tumor assessment for the final evaluated subject in each cohort is delayed. At the time of the interim analysis for each cohort, enrollment into the respective cohort will be paused until the determination that criteria for advancement to Part 2 has been achieved. Note it is possible for the futility criterion to be passed before the above specified analysis timing. These analyses will be conducted based on BICR assessment in the FAS.

Cohort 1 Decision Criteria at Interim:

1. If at least 3 responders out of 24 subjects in Cohort 1 are observed, then further enrollment in this cohort may proceed.
2. If 0 or 1 responder out of 24 subjects in Cohort 1 is observed at the interim, then further enrollment in this cohort may stop.
3. If 2 responders out of 24 subjects in Cohort 1 are observed, then a decision will be made, after further review of the data, to either continue or stop further enrollment in this cohort.

Cohort 2 Decision Criteria at Interim:

1. If at least 2 responders out of 12 subjects in Cohort 2 are observed, further enrollment in this cohort may proceed after submission of a protocol amendment which includes the preliminary data from Cohort 2 Part 1.
2. If 0 responder out of 12 subjects in Cohort 2 is observed at the interim, then further enrollment in this cohort may stop.
3. If 1 responder out of 12 subjects in Cohort 2 is observed, then a decision will be made, after further review of the data, to either continue or stop further enrollment in this cohort. Further enrollment will be contingent upon submission of a protocol amendment which includes the preliminary data from Cohort 2 Part 1.

The exact decision rules will depend on the actual number of subjects at the respective interim analysis.

If the criterion to pass futility is met at interim for Cohort 2 but not Cohort 1, all data will be reviewed thoroughly to decide the next step for the study.

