The criterion for interim analysis is constructed as follows: based on the interim data, if in a cohort there is less than 10% probability for the true ORR to be above 20% (clinically meaningful ORR), then U3-1402 is considered futile in this cohort and further enrollment may not be warranted. If there is at least 10% probability for the true ORR to be above 20% and at least 80% probability for the true ORR to be above 5% (ORR based on historical data)^{9,10} then promising efficacy is demonstrated in this cohort and further enrollment in this cohort may proceed.

If the true ORR is 20%, then the probability of observing at least 3 responders out of 24 subjects in Cohort 1 at the interim analysis will be 88.5% and the probability of observing at least 2 responders out of 12 subjects in Cohort 2 at the interim analysis will be 72.5%. If the true ORR is 5%, then the probability of observing 0 or 1 responder out of 24 subjects in Cohort 1 at the interim analysis will be 66.1% and the probability of observing 0 responders out of 12 subjects in Cohort 2 at the interim analysis will be 54%.

The determination of whether to advance a cohort to Part 2 of the study may also take into consideration the PK properties of U3-1402 among subjects enrolled in this study, and the subject or disease characteristics of enrolled subjects, among others. The decision to advance the study to Part 2 might be deferred based on the collective evaluation of such information. If indicated, the Sponsor may amend the protocol to evaluate other doses, dose regimens, or selected subject populations with advanced or metastatic CRC prior to advancing the study to Part 2.

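### Does Section 11.3 force a stop at interim counts where Section 11.6 leaves the decision open?

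*Combined protocol and SAP*

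**What the plan says.** Section 11.3 follows Table 11.1 with "If the criteria to continue enrollment are not met at interim futility analysis in either cohort, further enrollment will be stopped". It then gives the resulting size: "In this scenario, the total sample size for the study will be approximately 36 subjects (Cohort 1: 24 subjects, Cohort 2: 12 subjects". It does not define the criteria it refers to and mentions no responder counts.

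Section 11.6, repeated in the synopsis, sets three bands for each cohort:

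- **Proceed:** at least 3 of 24 in Cohort 1, at least 2 of 12 in Cohort 2. Enrolment may go on, in Cohort 2 only after a protocol amendment.
- **Stop:** 0 or 1 of 24, or 0 of 12: "then further enrollment in this cohort may stop".
- **Review:** 2 of 24, or 1 of 12: "a decision will be made, after further review of the data, to either continue or stop further enrollment in this cohort". For Cohort 2, continuing again needs an amendment.

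Section 11.6 also holds enrolment during the look: "enrollment into the respective cohort will be paused until the determination that criteria for advancement to Part 2 has been achieved". In explaining how the counts were built, it says that when a true ORR above 20% is too improbable, "then U3-1402 is considered futile in this cohort and further enrollment may not be warranted".

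**The concern.** Read by itself, the Section 11.3 sentence is a binding rule: miss the criteria in both cohorts and the study ends at about 36 subjects. Section 11.6 nowhere says that enrolment must stop. If the criteria in Section 11.3 are the proceed counts, then 2 of 24 with 1 of 12 ends the study under one section and leaves it open under the other, with up to 44 further subjects at stake (36 against 80). The sentence that pauses enrolment until criteria are achieved seems to support the binding reading. The disagreement would also matter most when the drug does no better than the 5% historical rate, which is the case a futility look is meant to catch.

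**Working it through.** **Inputs.** n = 24 and 12, the bands above, and reference ORRs of 5% and 20% (Sections 11.3 and 11.6). Assumptions: exact binomial counts, independent cohorts, the same true ORR in both.

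**The plan's own figures reproduce.** P(X ≥ 3 | 24, 0.20) = 88.55% (printed 88.5%). P(X ≥ 2 | 12, 0.20) = 72.51% (72.5%). P(X ≤ 1 | 24, 0.05) = 66.08% (66.1%). P(X = 0 | 12, 0.05) = 54.04% (54%).

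**Meaning of *either*.** The attached total of 36 is 24 + 12, and Scenario 2 of Table 11.1 lets Cohort 1 continue when Cohort 2 stops. The sentence therefore covers only the case in which neither cohort continues.

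**Band probabilities (stop / review / proceed).**

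| True ORR | Cohort 1 | Cohort 2 |
|---|---|---|
| 5% | 0.6608 / 0.2232 / 0.1159 | 0.5404 / 0.3413 / 0.1184 |
| 10% | 0.2925 / 0.2718 / 0.4357 | 0.2824 / 0.3766 / 0.3410 |
| 20% | 0.0331 / 0.0815 / 0.8855 | 0.0687 / 0.2062 / 0.7251 |

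**Widest possible divergence at 5%.**

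- Neither cohort proceeds: (0.6608 + 0.2232) × (0.5404 + 0.3413) = 77.9%.
- Both at stop counts: 0.6608 × 0.5404 = 35.7%.
- The difference is 42.2%: neither cohort proceeds and at least one is at a review count. The same difference is 28.9% at 10% and 2.9% at 20%.

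**Part of it that could open Part 2 as written.** Both Part 2 scenarios in Section 3.1 and Table 11.1 need Cohort 1 to go on. Cases with Cohort 1 at 0 or 1 and Cohort 2 at 1 have no Part 2 scenario, and enrolling more in Cohort 2 would need an amendment. At 5% these are 0.6608 × 0.3413 = 22.6% and drop out. What remains is Cohort 1 at exactly 2 with Cohort 2 at 0 or 1:

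- 5%: 0.2232 × (0.5404 + 0.3413) = 19.7%
- 10%: 0.2718 × (0.2824 + 0.3766) = 17.9%
- 20%: 0.0815 × (0.0687 + 0.2062) = 2.2%

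So at 5%, if stop counts stop and every 2 of 24 continues, the chance of ending at 36 is 77.9% − 19.7%, which is 58.3% before rounding of the terms. It does not fall to 35.7%.

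**Effect on printed results.** Table 11.2 gives P(X ≥ 8 | 68, 0.05) = 2.0% and P(X ≥ 9 | 80, 0.05) = 1.8%. Both reproduce as single-stage binomials (0.0200 and 0.0184) with no interim term, so they are the same whether the interim rule binds or not. Within each scenario, reaching the final count and also passing the interim cannot be more probable than reaching the final count.

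**The case for a change.** The best argument for a change is about conduct. The study is open-label, the sponsor takes the decision, and the only committee described (Section 13.2.5) is for interstitial lung disease. The SAP need only be final before database lock, so the protocol text may be all that governs the interim. Section 13.2.9 allows no deviations except for immediate hazards, so whether opening Part 2 after 2 of 24 complies ought to be clear from the text. The amendment requirement covers Cohort 2 only. A case-by-case review is also hard to describe as a criterion that is met, which makes the proceed counts a natural reading of Section 11.3.

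Part of this stands. *Will* and *may* do disagree at the stop counts, however the criteria are read, and the pause sentence is loosely worded. But the text does show which section governs. Section 3.1 and the synopsis base the Part 1 decision on the criteria in Section 11.6. The notes to Figure 3.1 send futility details to Section 11.6 and only the Part 2 sample size to Section 11.3. Within Section 11.6 the review counts are themselves numbered items among each cohort's decision criteria, for example "If 1 responder out of 12 subjects in Cohort 2 is observed, then a decision will be made", so a review that ends in continuing can satisfy them and lift the pause.

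A related point is that the paragraph on how the counts were built gives no action between its futile zone and its promising zone (the latter needing, among other things, "at least 80% probability for the true ORR to be above 5% (ORR based on historical data"). The numbered review item already supplies that action. Whether 2 of 24 falls in that gap also depends on a method the plan does not name. A one-sided binomial tail gives 11.5% against the 10% futility limit; a uniform prior, taken as an assumption, gives 9.8%.

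**Conclusion.** No change to the plan is needed. The Section 11.3 sentence is a sample-size summary for the stop-in-both-cohorts row that Table 11.1 omits, written more firmly than the rule it summarises. Section 11.6 states a discretionary futility rule, which is a legitimate choice in a study that plans no statistical testing (Section 11.2). Making it binding would be a trade-off and not a correction: at a true ORR of 20%, sending every 2 of 24 to stop lowers the chance that Cohort 1 continues from as much as 96.7% to the printed 88.5%.

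On the stricter reading of Section 11.3, the divergence within the present Part 2 scenarios is 19.7% at a true ORR of 5%, 17.9% at 10% and 2.2% at 20%. These figures assume exactly 24 and 12 subjects, independent cohorts with equal ORR, stop counts that stop, and reviews that always end in continuing. They are therefore the most that could be affected under those assumptions. Aligning the wording when the protocol is next amended would be tidy, but it would alter no printed probability, estimate or conclusion.
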